## Visits

**Data Collection Visit One:** The data collector will call or do video visit with patient in order to re-screen for criteria to be in the study. If participant meets criteria, the data collector will have participant sign a consent form.

We will be using DocuSign, the Institution's approved and 21 CFR Part 11-compliant software, to obtain a secure electronic signature. Once the IRB approves our consent form(s), we will use the IRB-approved consent form(s) as the base for the DocuSign template. The IRB-approved document will not be altered other than to overlay locations where signatures, initials, dates or other DocuSign fields will be added to create the study-specific DocuSign template.

We will send the consent to the participant via DocuSign, providing a participant-specific code in advance of sending the document via DocuSign, that will be required when the participant accesses and signs the consent. The consent discussion may take place via phone or video conference (e.g. Zoom). Participants will be given adequate time to consider the research study and ask questions prior to signing the consent form. When ready to sign, the participant will enter their code, verifying that the person signing the consent is the person that we spoke with previously, and sign the consent within the DocuSign system.

(Note: For studies requiring multiple signatures, e.g. two parental signatures or if a witness is required, all individuals will receive codes in order to sign). Once the participant has electronically signed, the study team member obtaining informed consent will be notified that the electronic form is ready for his or her signature. Once signing is completed by all parties, both the study team and the participant can download the signed consent as a PDF. The study team will also have access to the audit log and the Certificate of Completion. The study team will load the signed consent into Epic.

After the informed consent process is completed, the IRB approved study team member files the consent document in the research record, including a note confirming the consent process. The data collector will verify if the participant has any questions regarding the consent form and verify the participant understands the consent form. The data collector will ensure that the participant reads the consent form and has a copy of the consent form. After the consent is completed, a formal assessment of outcomes will be done. The data collector will explain the process of saliva sample collection to the participant. We will not collect saliva samples from participants outside of Maryland. A kit will be dropped off to the participants with non-contact either at their door or given to front office. We will call and confirm participants receive the kits. The participants will be asked to store samples in their home refrigerator. If there is not a working refrigerator, the participants will be provided with a cooler and ice packs that will be replaced over the two days. When the participant is ready for the saliva sample to be picked up, they will notify us, and it will be picked up using protective gear (gown, gloves, and mask) without contact with participants and stored in the Johns Hopkins School of Nursing lab.

**Final Data Collection Visit:** At this visit, the data collector will enact the same protocol as at baseline.

**Saliva Sample Visits:** A member of the research staff will contact the participants to ask them a good time to pick up samples. The research staff member will arrive to participants home to pick up samples. Personnel picking up the samples will notify participants when they are arriving, and participants will place the sample outside the front door once the staff member pulls up or walks up to their home location. The staff member will label the specimens and take them directly to the Johns Hopkins School of Nursing refrigerator. Please see specifics below (laboratory studies) for further information about the collection and storage process of the saliva samples.

**Nurse Visit One:** The first nurse visit via Zoom video/call will consist of the nurse conducting an assessment of the participant's mental and physical health. The nurse will conduct education on depressive symptoms and pain. A booklet on both depression and pain will be left with the participant (see the intervention manual). This will be emailed or mailed to participants. Next, the nurse will assist the participant to set goals surrounding pain and depressive symptoms, and determination of strategies to be practiced for the next six visits.

After the participants have selected the goals the nurse will work with them to develop a plan of strategies. The strategies that the nurses will offer to work on with the participants will be evidenced-based and specifically target goals surrounding pain and depressive symptoms. For example, if a participant identifies she has arthritic pain the nurse would offer strategies effective for this type of pain such as heat therapy. If the participant agrees to this strategy, the nurse will identify the safest mechanism of heat therapy (e.g. warm gel packs) for the participant. The nurse would identify any contraindications (e.g. diabetic neuropathy). If no contraindications are identified, the nurse would purchase the gel packs using the funding for the study and would mail the packs to the participants. The nurse would teach the participant how to use the gel packs and then use the teach back method with the participant to ensure they know how to use them safely. This would be done via video visit. The participant would be able to call the nurse or PI with any questions or difficulties using any of the strategies. Examples of the strategies we plan to use include heat packs, tai chi exercises,  breathing exercises, and training in communication with health care providers surrounding pain and depressive symptoms. The strategies will be individualized to meet the goals of the participants; however, the fidelity of the intervention will be maintained by the nurses being consistent in how the intervention is delivered and the structure of the visits. All participants will also have the same outcome measures.

**Nurse Visits Two and Three:** The next two visits will consist of the nurse working through each of the strategies. The nurse will discuss strategies with participants via video visits. The nurse will tailor the strategies and teach the participant the strategy at visits two and three.

**Nurse Visit Four:** At visit four the nurse will observe the participant performing the strategies (e.g. completing exercises in the home), discuss how the strategies are going, and reevaluate goals. Any accommodations or changes will be made at this visit.

**Nurse Visit Five:** At visit five the nurse will observe the participant doing strategies and assist with any changes.

**Nurse Visits Six and Seven:** At visits six and seven the nurse will evaluate the participant working on strategies and remind them of their goals.

Nurse Visit Eight: At visit eight the nurse will conduct a final assessment and goals will be assessed at that time. The nurse will reevaluate the goals with participants and ask them if they believe they met their goals, why or why not.

**Measurements:** We chose measures based on our experiences in community-based trials as well as those that met the following criteria: 1) possess known reliability and validity with older samples; 2) are sensitive to change from an intervention; 3) represent objective as well as subjective indicators of the domains we seek to impact. Finally, we sought to achieve a balance between psychometric quality and practical considerations such as respondent burden. Table 1 shows the instruments that will be used to measure outcomes.

**Table 1- Instruments Measuring Main Outcome Variables**

Outcomes	Instruments
Cognition (see inclusion/exclusion criteria)	Short Portable Mini Mental Status Exam 
Depressive Symptoms	Patient Health Questionnaire 9 and Patient Reported Health Outcomes (PROMIS) 57 
Pain	PROMIS Pain Interference, Pain Intensity and Pain Behavior 
Communication	Patients' Reaction Assessment 
Comorbid Conditions	Charlson Comorbidity Index 
ADLS/IADLS	Katz 
Frailty	Frailty phenotype  Frail Scale  will be used to measure frailty.
Stress	Perceived Stress Scale 
Self-Efficacy	Coping and Self-Efficacy Scale 
Readiness to Change	Gitlin and Rose's Readiness to Change Rating System (Gitlin & Rose, )
Social Network Scale	Lubben Social Network Scale
IL6	Saliva Sample
TNF $\alpha$	Saliva Sample
IL8	Saliva Sample
IL-1 $\beta$	Saliva Sample
Goal Attainment	Subjective Report

The following instruments and a demographic questionnaire (e.g. age, SES, and education) will be administered to the participants' pre- and post-intervention.

#### Outcomes:

**Depressive Symptoms:** During the delivery of this intervention, we will use two instruments the PHQ 9 and the PROMIS. We will use the PHQ 9 to measure depressive symptoms. The PHQ9 includes 9 questions related to the DSM diagnostic criteria for major depression. We will also use the Patient Reported Outcomes Measurement System (PROMIS) 57, which is an 8-item instrument that can be used to measure self-reported negative mood, view of self, and somatic symptoms. Utilizing both measures will

Date: 09/17/2024

Principal Investigator: [name], RN, FAAN

Application Number: IRB00226182

ensure we obtain an in-depth measure of depressive symptoms in our sample. These instruments that are easily transferrable to the clinical setting.

**Pain:** Pain interference will be measured using the PROMIS Pain interference scale, which consists of six items from the PROMIS short form on pain interference. The scores range from 6-30 with higher scores indicating more pain interference. Pain intensity will also be measured using one item from PROMIS Pain Intensity Instrument. Scores range from 0-10 and higher scores indicate more intensity. The PROMIS pain behavior scale is used to measure self-reported external manifestations of pain. The scores on PROMIS Pain Behaviors scale can range from 7-42 with higher scores indicating more pain behaviors.

**Communication:** The participants' perceived abilities to initiate communication with their primary health care providers will be measured using the Patients Reactions Assessment (PRA). The PRA is a 15-item instrument used to measure the quality of patients' relationships with their health care providers and includes a subscale on the ability to initiate communication. The subscale on the instrument that measures perceived ability to communicate will be used; scores can range 0-35 with higher scores indicating higher perceived ability to communicate.

**Comorbid Conditions:** We will measure comorbid conditions with the Charlson Comorbidity Index. The Charlson comorbidity index consists of 17 categories of chronic conditions including two subcategories for diabetes and liver disease. Comorbidities are based on mortality risk and severity of the disease; the scores for each disease range from 1-6. A final Charlson Comorbidity Index score is compiled; scores greater than or equal to five indicate more chronic conditions and increased risk of mortality.

**Physical Function:** Physical function will be assessed by measuring ADLs Katz ADL and Lawton's IADL measures. On Katz's ADLs scores range from 0-6 with 6 indicating full function and a score of 2 or less indicating sever functional impairment. On Lawton's IADL instrument scores range from 0-8 and higher scores indicate better physical function.

**Frailty** will be assessed by the physical frailty phenotype (includes gait speed, grip strength, BMI, and measures of physical activity and exhaustion). The frailty phenotype is used to determine if a person is robust (score of 0), pre-frail (score of 1 or 2), or frail (score of 3-5). The Frail Scale will be used to measure frailty for virtual data collection visits. The Frail Scale asks self-report questions about fatigue, resistance, ambulation, illnesses, and loss of weight.

**Stress** will be measured by perceived stress as it often accompanies depression and/or pain. We will measure using the perceived stress scale. The scores can range from 0-40; higher scores indicate more perceived stress.

**Self-efficacy** is a large part of self-regulation. We are going to measure self-efficacy using the coping and self-efficacy scale. The scores range from 0-26 with higher scores indicating more self-efficacy.

**Readiness to change** will be used to identify participants' readiness to change. The levels include 1-pre-contemplation, 2-contemplation, 3- preparation, and 4- action and maintenance. This will allow the nurses to identify where participants are on this scale and determine if strategies or goals need to be adjusted or reevaluated based on readiness to change scores.

**Social Networks** may be related to depressive symptoms and/or stress. We will measure social networks through the Lubben social network scale, which identifies social engagement with both family and friends. The scores can range from 0-60 with higher scores indicating more social engagement.

There is a growing body of literature demonstrating the relationship between inflammatory cytokines with pain, frailty, and depression. For example, inflammatory cytokines may play a very crucial role in pain transmission pathways. Studies have shown a link between frailty as well as pain with IL-6 and Tumor Necrosis Factor Alpha. The release of pro-inflammatory cytokines can lead to neuro inflammation, which can contribute to depression.

We describe the cytokines we will measure below:

**Interleukin-8 (IL-8):** IL8 is a pro-inflammatory cytokine that is used for neutrophil recruitment. It may increase with pain and depression.

**Interleukin - 1 $\beta$  (IL- 1 $\beta$ )** IL 1 $\beta$  is a pro-inflammatory cytokine that affects cell vial binding cell surface IL-1R1 receptor. It increases neuronal excitability and may increase with pain and frailty.

**Interleukin -6 (IL-6)** is a pro-inflammatory cytokine that functions in inflammation and maturation of B cells. It is associated with an increase in pain, frailty, and depression.

**Tumor Necrosis Factor-Alpha (TNF- $\alpha$ )** is a pro-inflammatory cytokine which stimulates the NF- $\kappa$ B signaling pathway resulting in down-stream IL-6 production. It is associated with an increase in pain and frailty.

**Goal Attainment** will be measured by asking participants if their goals are not met, partially met, or fully met. We will evaluate goal attainment at nurse visit five as well as the final visit (nurse visit 8).

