### **1. Abstract**

Older African American women experience disproportionate rates of chronic conditions in comparison to other groups. Pain, depressive symptoms, and frailty often co-occur in African American women aging with chronic conditions and this combination can lead to disability and poor quality of life. Addressing pain and depressive symptoms may improve or delay the progression to frailty. To our knowledge there is little work being done in this population to address both pain and depression. The Depression and Pain Perseverance through Empowered Recovery (DAPPER) program is person directed and will consist of 8 nurse visits during which the nurse assesses each participant for pain, depression, and frailty, then implements a manualized individually tailored intervention. The data collection visits, and nurse visits will take virtually. We propose a pilot trial that is a wait list randomized control pilot to test the acceptability and obtain a preliminary effect size for the intervention. We will recruit 64 ( $\geq$ age 50) African American women who report pain intensity of 3 or higher that interferes with their activities, depressive symptoms lasting more than two weeks, are pre frail or frail, and live in the community/are not institutionalized. The sample will be recruited through the PI's previous study, community recruitment flyers distributed virtually, and word of mouth campaigns. Participants will be randomized into either the intervention or the wait list control group. Once the intervention group has completed their visits, the wait list control group will begin their visits. All participants will be offered the same information and format of nurse visits. The nurses will systematically tailor the content of the visits to the participants' risk profile and goals based on protocols. All participants will be assessed at the start of the study, at 12 weeks, and 24 weeks. The primary outcomes will be pain, depressive symptoms, and frailty status. Other endpoints include goal attainment, stress (cytokines), self-report, self-efficacy, and communication with health care providers. We will also examine the acceptability of the intervention using intervention compliance and one-on-one qualitative interviews. This study will offer either virtual or in person visits based on the preference of the participants.

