### **2. Objectives**

The aims of this pilot project are to 1) test the Depression and Pain Perseverance through Empowered Recovery (DAPPER) program for feasibility and acceptability. Specifically, we will 1) test the effect size of DAPPER on pain and depressive symptoms from baseline to 12 weeks (compare intervention to wait list control group) and then at 24 weeks to compare the intervention group to wait list control group once again, 2) estimate preliminary effect sizes for DAPPER in reduction of frailty, and 3) measure effect sizes and feasibility of measuring cytokines.

This study is being supported through funding from the Harold Amos Medical Faculty Program and the Johns Hopkins Older Adults Independence Pepper Center.

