### Approach

**4.a Theoretical Framework:** Self-regulation theory is the theoretical framework for this study. Self-regulation theory involves two tenets: 1) participants manage their response based on their experiences (experiences with pain, depression, and frailty treatments) and knowledge of an event and 2) participants' goals are to maintain comfort and decrease the negative effects of an illness (pain depression and/or frailty) on their lives. The intervention is participant centered and participant driven. This means that the participants' experiences and existing knowledge about pain, depressive symptoms, and frailty will drive the goals that they set. For example, a participant may have experienced pain, depression symptoms, and frailty; she is no longer able to go work in her garden. Her goal may be to be able to garden again. This would provide comfort, decrease the effects of these three conditions, and potentially improve her symptoms.

**Design overview of the study:** The design of the study is outlined in the above figure. The outcomes will determine effect sizes on the intervention's effect on pain and depressive symptoms. Outcomes will be measured at 12 weeks (compare intervention and wait list control group) and at 24 weeks (look at outcomes for wait list control group and outcomes over time for intervention group). Goal attainment will be measured at 12 weeks and 24 weeks. At 24 weeks, we will also conduct virtual semi-structured one on one individual interviews with participants to determine feasibility and acceptability.

The intervention group (n=30) will start the study and will receive eight nurse visits that will be focused on decreasing pain, depressive symptoms, and meeting participant selected goals set in these areas. The wait list control group will receive monthly calls by a study team member to ensure their contact information

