has not changed. Data collection, nurse visits, and interviews will be completed via Zoom video calls. Zoom is a HIPAA compliant virtual meeting software used for telehealth purposes. The study will include either in person or virtual visits depending on the preference of the participants. The study team completing in person visits have all been fully vaccinated and will wear personal protective equipment at visits. In addition, study team will screen all research participants for symptoms of COVID based on the Johns Hopkins University of Medicine including fever, cough, sore throat, shortness of breath, acute loss of taste or smell, headache, vomiting or nausea, new fatigue or runny nose in the last 72 hours. The study team will reschedule if participants exhibit any of these symptoms at a later date when participants are symptom free for 72 hours or have a negative Covid-19 test.

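### Frailty is named a primary outcome and has its own aim, but the sections conflict on which instrument measures it, and no frailty analysis is planned

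*Combined protocol and SAP*

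**What the plan says.** **Status of the outcome.** Section 1 (Abstract): "The primary outcomes will be pain, depressive symptoms, and frailty status". Section 2 (Objectives) lists, as a specific aim, to "estimate preliminary effect sizes for DAPPER in reduction of frailty".

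**Instrument.**
- Inclusion/Exclusion Criteria, criterion 5: pre-frail and frail are defined only by the number of phenotype criteria met.
- Data Collectors paragraph: the first visit is a Zoom call. The collector completes the phenotype measurements there, and enrolment continues only if the frailty, pain and depression criteria are met.
- Outcomes, Frailty paragraph: the phenotype includes gait speed and grip strength and has cut-offs (0 robust, 1-2 pre-frail, 3-5 frail). It then adds: "The Frail Scale will be used to measure frailty for virtual data collection visits". For that scale it lists the self-report domains but no score or cut-off.
- Table 1 lists both instruments without saying when each applies.

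**Visit mode.** The Abstract says "The data collection visits, and nurse visits will take virtually" and also "This study will offer either virtual or in person visits based on the preference of the participants". The Approach section says "Data collection, nurse visits, and interviews will be completed via Zoom video calls" and, shortly after, "The study will include either in person or virtual visits depending on the preference of the participants". The Final Data Collection Visit paragraph repeats the baseline procedure but does not expressly fix mode or instrument for a participant.

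**Analysis.** The design overview ties effect sizes to the intervention's "effect on pain and depressive symptoms. Outcomes will be measured at 12 weeks". Section 5, Analytic approach, names pain, depressive symptoms and communication with providers as the outcomes and fits GEE to depressive symptoms and pain. Frailty does not appear there.

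**The concern.** This pilot's product is a set of effect sizes for planning a definitive trial; section 5 expressly disclaims power. A frailty effect size is useful only if the reader knows which instrument produced it, in whom, and in what form (score or category). As written, three things are open.

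1. At a virtual baseline, one section calls for the phenotype and another for the Frail Scale. Criterion 5 is worded for the phenotype only, so it is unclear how it would be verified under the second.
2. If participants use different modes, the Outcomes rule gives them different instruments, one partly performance-based and one wholly self-report.
3. With no frailty analysis stated, the instrument and the form of the variable could be chosen after the data are seen.

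**Working it through.** **Step 1. Can a virtual baseline establish criterion 5?** Criterion 4 places the first data collection visit on video. The recruitment text and Data Collection Visit One re-screen by video or call, and randomisation follows only for those who qualify after that visit. Two readings are possible:
- Under the Outcomes section, the instrument is the Frail Scale. Criterion 5 counts phenotype criteria, and no mapping from one to the other is given.
- Under the Data Collectors paragraph, the instrument is the phenotype, by Zoom. No method is given for obtaining gait speed or grip strength by video.

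The assignments conflict, and neither is operational as written.

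**Step 2. Does one instrument cover the between-group contrast?**
- If all data collection is virtual, the Outcomes section gives a single instrument and nothing is mixed, but the protocol states no status cut-offs for it.
- If participants choose, the instrument follows the choice. Repeating the baseline procedure at the final visit may be meant to keep the instrument constant within a person. It would not make it the same across people.

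**Step 3. Is frailty analysed?** It is in the Abstract's primary outcomes and the Objectives, but not in the outcome list or the GEE outcomes of section 5. No variable form, link or effect measure is given.

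**Step 4. What would separate reporting cost in precision?** The only sample-size figure available is section 5's count after attrition. It does not reproduce: 64 x (1 - 0.13) = 55.7, against 52 stated, while the arms shown give 25 + 25 = 50. I use 25 per arm for scale only.

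If a share s of completers in each arm has a given instrument, the 95% interval relative to giving that instrument to everyone is wider by 1/sqrt(s) (normal approximation, same SD in the subset):

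| Assumed share s | Completers per arm (25 x s) | Width factor |
|---|---|---|
| 0.75 | 18.75, about 19 | 1/sqrt(0.75) = 1.15 |
| 0.50 | 12.5, so 12-13 | 1/sqrt(0.50) = 1.41 |
| 0.25 | 6.25, about 6 | 1/sqrt(0.25) = 2.00 |

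The normal approximation is too small in the last row. With t critical values (10 df for 6 per arm, 48 df for 25 per arm): sqrt(25/6) x 2.228/2.011 = 2.04 x 1.108 = 2.26.

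The 1/sqrt(s) factors do not depend on section 5's inconsistent counts; the t-based figure does. The shares are not in the documents.

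**The case against.** **The Outcomes section is a rule by mode.** Taken alone, it is. Criterion 5 and the Data Collectors paragraph contradict it. The Fidelity Plan (staff trained in the phenotype) and the risk section (walking-speed test) show that the phenotype remains a working procedure.

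**A reader might infer that no frailty assessment is defined at a virtual baseline.** The documents do not support that: two are assigned, and they conflict.

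**The Frail Scale's scoring may be in the cited source.** That is possible. The protocol also omits score ranges for the PHQ-9. What stands is narrower: the protocol states no mapping from the scale to criterion 5 or to frailty status.

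**Only the Abstract calls frailty primary.** True, and the Background speaks of frailty as a hoped-for effect. Dropping the label could reconcile the outcome lists. The aim in the Objectives would still need an analysis.

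**A reader might infer that the plan pools the two instruments and so biases the result.** No section plans a pooled frailty estimate, and no bias is shown. The point is that nothing prevents pooling and no common instrument is assured.

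**It is only a pilot.** Low power excuses wide intervals. It does not excuse leaving open what the effect size measures.

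**Conclusion.** The concern holds as a conflict between sections plus an omission. Criterion 5, the Data Collectors paragraph, Table 1 and the Outcomes section do not agree on the frailty instrument; visit mode is stated two ways; and a stated aim has no planned analysis. If both modes occur, following the Outcomes section means no single instrument covers the between-group contrast.

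The size and direction of any bias cannot be determined: the documents give no share of virtual visits and no frailty SD. The width factors of about 1.15 to 2.00 (2.26 with t at 6 per arm) are approximate illustrations under assumed shares of 75% to 25%. It would go too far to say that ineligible participants were enrolled; the documents show only that verification of criterion 5 at a virtual baseline is unclear. The sponsor should correct this, since the changes are cheap and both a named primary outcome and an eligibility criterion are affected.

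**What to change.** 1. Give the Frail Scale to every participant at every assessment whatever the mode, record the mode, and state the score and status cut-offs to be used.
2. Do not pool the two instruments. Report effect sizes by instrument and name the main one in advance. That choice is the sponsor's: the Frail Scale would cover everyone but is wholly self-report, whereas the Measurements paragraph wants objective indicators too. The phenotype matches criterion 5 but, if the Outcomes rule stands, would exist only for those seen in person.
3. Reconcile criterion 5, the Data Collectors paragraph, Table 1 and the Outcomes section, including how criterion 5 is assessed at a virtual baseline. Settle visit mode in the Abstract and Approach, and reconcile the outcome lists in the Abstract and section 5.
4. Add frailty to the planned GEE (time, group and their interaction) with one pre-stated form of the variable, score or category. Report the baseline-to-12-week effect size with its 95% CI.

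**Cost.** A few extra self-report questions at in-person visits, one recorded field, and wording. After baseline those questions are answered by participants who know their assignment; at baseline they do not, because randomisation follows the baseline interview.
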